SPIDER Study Protocol

Study Title

SPIDER – *Spinal Dural Arteriovenous Fistula International Data and Outcomes Registry*

Principal Investigator

[name], FAANS, FACS, FAHA

The [name] Distinguished Professor of Neurological Surgery and Radiology

Division Chief of Neurovascular Surgery & Endovascular Neurosurgery

Thomas Jefferson University Hospital

Study Coordinator / Contact

[name] [name]

Research Fellow, Department of Neurosurgery

Thomas Jefferson University Hospital

Study Version and Date

Version 1.0 – 20 December 2025

Background and Rationale

Spinal dural arteriovenous fistulas (SDAVFs, type I spinal vascular malformations) are the most common spinal vascular malformation but remain frequently underdiagnosed due to their insidious onset and nonspecific clinical presentation. Delayed diagnosis is common and often results in progressive, and sometimes irreversible, myelopathy. Despite advances in imaging and treatment, there remains significant variability in diagnostic timelines, treatment strategies (endovascular, surgical, or combined), and reported outcomes across institutions.

Existing literature is largely limited to single-center retrospective series or small cohorts, often underpowered to evaluate predictors of outcome, recurrence, and the impact of diagnostic delay. Furthermore, direct comparisons between treatment modalities and long-term functional outcomes using standardized clinical scales are limited.

The SPIDER registry is designed to address these gaps by creating the largest international, multicenter dataset of patients with spinal dural AVFs. By pooling de-identified data from high-volume centers worldwide, this study aims to provide robust, generalizable evidence to inform clinical decision-making and optimize patient outcomes.

Study Objectives

Primary Objectives

1. To characterize the clinical, radiological, and angiographic presentation of spinal dural AVFs.
2. To compare treatment strategies (endovascular, surgical, combined, or conservative management) and their angiographic and clinical outcomes.
3. To evaluate long-term neurological and functional outcomes following treatment.
4. To assess the impact of diagnostic delay on neurological status and long-term outcomes.

Secondary Objectives

- To identify factors associated with treatment failure or recurrence.
- To evaluate complication rates associated with different treatment modalities.

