- To explore predictors of functional recovery using standardized outcome measures.

Study Design

This is an **international, multicenter, retrospective observational cohort study**.

Participating centers will contribute de-identified data on patients diagnosed with spinal dural arteriovenous fistulas who were evaluated and/or treated at their institution.

No interventions will be performed as part of this study. All data are derived from existing medical records, imaging, and procedural reports.

Study Population

Inclusion Criteria

- Patients of any age diagnosed with **spinal dural arteriovenous fistula (Type I)**.
- Diagnosis confirmed by spinal angiography, MRI findings consistent with SDAVF, and/or operative findings.
- Patients managed with endovascular treatment, open surgery, combined approaches, or conservative management.
- Both symptomatic and incidental/asymptomatic cases.

Exclusion Criteria

- Intramedullary spinal vascular malformations (e.g., glomus AVMs, juvenile AVMs).
- Perimedullary AVFs or other non-dural spinal vascular lesions.
- Cases lacking sufficient data to confirm diagnosis or treatment details.

Data Collection and Variables

Each participating center will extract data using a standardized spreadsheet with predefined categorical options to ensure consistency across sites. All data will be fully de-identified prior to submission.

Demographics and Center Information

- Country

- Study center (institution name)
- Patient study number
- Age at diagnosis
- Sex

Clinical History and Presentation

- Months from symptom onset to diagnosis
- Misdiagnoses prior to SDAVF diagnosis
- History of spinal trauma
- Incidental/asymptomatic presentation
- Presentation with rupture (spinal, intracranial, both, or none)
- Presence of myelopathy at diagnosis
- Presenting symptoms: back pain, radicular pain, sensory symptoms, motor weakness, spasticity

Functional Status at Diagnosis

- Modified Aminoff–Logue Scale (Gait)
- Modified Aminoff–Logue Scale (Bladder)
- Modified Rankin Scale (mRS)

Radiological and Angiographic Characteristics

- Laterality of fistula
- Spinal level of fistula (highest level if multilevel)
- Number of arterial feeders
- Highest and lowest arterial feeder levels (if multiple)
- Involvement of the artery of Adamkiewicz
- MRI findings (myelomalacia, cord edema, or T2 hyperintensity)

Treatment Details

- Year of treatment
- Time from diagnosis to first treatment
- Initial treatment modality:

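### No all-cases rule, case-finding period or case count is set, and the insufficient-data exclusion can be read to reach angiographic outcome, so success rates and the modality comparison are open to case-selection bias

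*Protocol*

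**What the plan says.** - **Who is contributed.** Study Design says centres send data on "patients diagnosed with spinal dural arteriovenous fistulas who were evaluated and/or treated at their institution". Neither this sentence nor the criteria ask for every such patient or for a consecutive series.
- **Period.** The first inclusion criterion opens with "Patients of any age diagnosed with" and names the lesion. No criterion gives a start or end date for diagnosis or treatment. The Timeline's deadline of end of February 2026 applies to data collection, not to eligibility.
- **Exclusion.** The last exclusion criterion is "Cases lacking sufficient data to confirm diagnosis or treatment details". It does not define sufficiency or say who applies the rule.
- **Extraction.** Under Data Collection and Variables: "Each participating center will extract data using a standardized spreadsheet with predefined categorical options to ensure consistency across sites". The next sentence adds: "All data will be fully de-identified prior to submission". Nothing in the protocol asks for a tally of cases found, excluded or submitted.
- **Outcome items under treatment.** Treatment Details lists the angiographic result of embolization and the surgical outcome (disconnection successful or not). Primary Outcomes includes angiographic success in three grades.
- **Calendar information.** The only calendar field is "Year of treatment". Conservative management appears under the same heading as an option for initial modality.
- **Ambition.** Background and Rationale promises "robust, generalizable evidence to inform clinical decision-making and optimize patient outcomes".

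**The concern.** In a retrospective registry, the rule for finding cases sets the denominator. Here a centre can follow the text and still send a subset of its eligible patients, and nobody downstream could tell how large that subset is or how it differs from the rest.

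The exclusion adds a more specific problem. If treatment details are read as the items under that heading, a case can be dropped because its angiographic or surgical result was not documented. Inclusion would then depend on whether a primary-outcome item is on file. It could do so differently by modality, since the endovascular and surgical item lists differ. Comparing modalities is the second primary objective.

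This is not a detail that a statistical analysis plan could settle later. The protocol's missing-data sentence can act only on rows that were submitted. Once collection closes, cases never sent and never counted cannot be imputed, weighted or bounded.

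**Working it through.** The protocol gives no expected rates, sample size or submission proportions, so there is no figure of its own to reproduce. All rates below are assumptions, used to show how the bias behaves.

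**1. One group, selection by outcome.** Let p be the true good-outcome rate, a the share of good-outcome cases submitted, and b the share of poor-outcome cases submitted.

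Observed rate = p·a / (p·a + (1 − p)·b)

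With p = 0.60 and a = 0.90:
- b = 0.90 (no selection): 0.54 / (0.54 + 0.36) = 0.600
- b = 0.80: 0.54 / (0.54 + 0.32) = 0.628
- b = 0.70: 0.54 / (0.54 + 0.28) = 0.659
- b = 0.50: 0.54 / (0.54 + 0.20) = 0.730

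Reverse direction, with a = 0.70 and b = 0.90: 0.42 / (0.42 + 0.36) = 0.538. The protocol gives no reason to prefer one direction.

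**2. Two modalities, both truly 60%.** Selection multiplies the observed odds by a/b.
- One modality selected at 90% v 70%, the other unselected: 0.659 v 0.600, a difference of 5.9 points; odds ratio 0.90 / 0.70 = 1.29.
- Both selected at 90% v 70%: the factor 1.29 cancels and the odds ratio stays at 1.00, although both rates are overstated.
- One modality selected the other way (70% v 90%): odds ratio 0.70 / 0.90 = 0.78.

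**3. Different assumptions, framed as omission.** Let m be the share omitted and q the rate among omitted cases. Observed rate = (p − m·q) / (1 − m). Take p = 0.80 and q = 0.40 in both modalities, with 5% omitted in one and 20% in the other:
- (0.80 − 0.02) / 0.95 = 0.821
- (0.80 − 0.08) / 0.80 = 0.900

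The spurious difference is 7.9 points. If q = p there is no bias at any m.

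**4. What a count would give.** With an observed rate o and a known m, the true rate lies between (1 − m)·o and (1 − m)·o + m. For o = 0.80 and m = 0.20, that is 0.64 to 0.84. Without a count, m is unknown and this interval cannot be computed.

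**5. Reach of the exclusion.** The criterion names diagnosis and treatment details. Angiographic and surgical results are listed under Treatment Details, so the criterion can reach them. Recurrence, mRS, Aminoff–Logue scores and clinical status sit under separate headings (Recurrence and Re-treatment; Follow-Up and Outcomes), so a missing value there does not trigger it. Those outcomes are exposed only through the lack of an all-cases rule.

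**The case against.** Several stronger readings are tempting, and the protocol does not support them.

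- **That sites are allowed to pick cases.** The protocol is silent, not permissive. The Study Design sentence can naturally be read as meaning all such patients, and the criteria expressly admit conservative and incidental cases. That lowers the risk but does not remove it, because nothing makes the all-patients reading binding or checkable.
- **That sites discard insufficient-data cases locally and uncounted.** The text does not say who applies the exclusion. The Timeline has a data-cleaning stage, so the main centre could apply it to submitted rows and count the losses. It could not count cases that were never sent.
- **That failures are filtered out.** Partial and unsuccessful occlusion, unsuccessful disconnection, worsened status and death are all recordable. Nothing shows that well-documented cases are the successful ones; referred failures could be better documented. The direction is open.
- **That every main estimate is a biased proportion.** Functional outcome uses ordinal scales, and diagnostic delay is studied as an association. The rate arithmetic fits success rates best.
- **That conservative cases carry no calendar year.** Their year field is ambiguous, not absent. For treated cases, year of treatment allows adjustment for period, so the missing window is secondary to the missing all-cases rule.

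The cost objection also has weight. The study is unfunded, and about ten weeks separate the protocol date (20 December 2025) from the collection deadline, so any added request must be short.

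**Conclusion.** The point holds in a limited form. The protocol requires neither all consecutive eligible cases nor a count of them and sets no period, and its completeness exclusion can be read to make inclusion depend on documentation of a primary-outcome item. Success rates and the modality comparison are open to selection bias; the documents do not show that it will occur, or how large it would be and in which direction.

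Under the assumptions above, moderate selection in one modality only produces a spurious difference of about 6 to 8 points. It produces no change in the odds ratio when selection is equal across modalities, and none at all when omitted cases resemble submitted ones. A reader should not infer that the registry's results are biased, or that the exclusion itself distorts recurrence or functional outcome. What is established is that the claim to generalizable evidence rests on a denominator nobody will be able to state. The change should be made while centres can still supply the information.

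**What to change.** 1. In Study Population, state that each centre submits all consecutive eligible patients diagnosed within a period that the centre declares before extraction.
2. Limit the last exclusion to cases in which the diagnosis or the initial treatment modality cannot be confirmed. Keep cases with an undocumented angiographic or surgical outcome and treat that item as missing data.
3. Have each centre return a short tally: cases identified, cases excluded by each criterion (with modality), and cases submitted. Centres that have already extracted can still be asked for this.
4. Add a year-of-diagnosis column, because the year-of-treatment field is ambiguous for conservatively managed patients.

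**Cost.** A protocol sentence, a reworded criterion, a brief tally and one spreadsheet column. The downside is modest extra work per site in a short, unfunded collection period, and some centres may have to declare a shorter period to meet the rule.

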 - Endovascular embolization alone
 - Open surgery alone
 - Combined approaches
 - Conservative management
- Endovascular details:

- Number of embolization attempts
- Embolic agent used
- Angiographic outcome
- Intra- or postprocedural complications
- Surgical details:
 - Intraoperative visualization modality
 - Indication for visualization
 - Surgical outcome (successful or unsuccessful disconnection)
 - Intra- or postoperative complications

Recurrence and Re-treatment

- Occurrence of recurrence
- Time to recurrence
- Treatment modality for recurrence
- Angiographic outcome after re-treatment

Follow-Up and Outcomes

- Duration of follow-up
- Symptom evolution at last follow-up (pain, sensory, motor)
- Modified Aminoff–Logue Scale (Gait and Bladder) at last follow-up
- Modified Rankin Scale at last follow-up
- Overall clinical status at last follow-up (improved, unchanged, worsened)
- Death, if applicable

Notes

- Additional relevant clinical or radiological comments

Outcomes

Primary Outcomes

- Functional outcome at last follow-up as measured by mRS and Modified Aminoff–Logue scales.
- Angiographic success (complete vs partial vs unsuccessful occlusion).

Secondary Outcomes

- Rate and predictors of recurrence.
- Complication rates by treatment modality.
- Association between diagnostic delay and neurological outcome.

Statistical Analysis Plan

Descriptive statistics will be used to summarize demographic, clinical, radiological, and treatment characteristics. Continuous variables will be reported as means with standard deviations or medians with interquartile ranges, as appropriate. Categorical variables will be reported as frequencies and percentages.

Comparative analyses will be performed to evaluate outcomes across treatment modalities using appropriate statistical tests (e.g., chi-square, t-test, ANOVA, or non-parametric equivalents). Multivariable regression models may be used to identify independent predictors of outcomes and recurrence.

Missing data will be handled using appropriate statistical methods depending on the extent and pattern of missingness.

Ethical Considerations

This study involves retrospective collection of **fully de-identified data** and poses minimal risk to participants. No direct patient contact will occur, and no protected health information will be shared.

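### The extraction list holds no comorbidity, pre-onset disability or reason-for-modality item, so adjusting the treatment comparison can reduce confounding by indication but not remove it.

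*Protocol*

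**What the plan says.** The protocol's second primary objective is "To compare treatment strategies (endovascular, surgical, combined, or conservative management) and their angiographic and clinical outcomes". The Study Design section describes an "international, multicenter, retrospective observational cohort study", so the modality was chosen in routine care. Under Data Collection and Variables, centres extract to a "standardized spreadsheet with predefined categorical options to ensure consistency across sites".

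The list under that heading contains:

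- **General history:** age, sex and "History of spinal trauma". The rest of the clinical history section concerns symptom duration, earlier misdiagnoses, incidental presentation, rupture, myelopathy and presenting symptoms.
- **Function before treatment:** the two Aminoff–Logue scales and the mRS, all under "Functional Status at Diagnosis".
- **Anatomy:** laterality, fistula level, number and levels of feeders, Adamkiewicz involvement and MRI findings.
- **Treatment:** "Initial treatment modality", year, and time from diagnosis to treatment. The only item on an indication concerns intraoperative visualisation, not the choice of modality.
- **Other:** country, centre and a free-text notes field.

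One primary outcome is "Functional outcome at last follow-up as measured by mRS" together with the Aminoff–Logue scales. Complications by modality are a secondary outcome. On adjustment, the Statistical Analysis Plan section says "Multivariable regression models may be used to identify independent predictors of outcomes and recurrence".

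**The concern.** In a cohort without randomisation, a comparison of modalities is only as good as the record of what drove the choice. Two plausible drivers are how fit the patient was for an operation or anaesthetic, and whether each modality was technically feasible. The mRS grades overall disability without attributing it to a cause, so poor general health can worsen the outcome whatever was done to the fistula. Complications plausibly depend on fitness too. Conservative management is the most exposed group: a patient too frail to treat and a patient who declined treatment receive the same code, with no reason recorded.

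This is a matter of data collection, not of analysis detail that a separate statistical analysis plan could supply. Such a plan can choose a better model, but it cannot adjust for a field that was not extracted. The protocol intends its results to guide treatment selection, so a residual difference between patients could be read as a difference between treatments. A large registry would add precision to that estimate without reducing its bias.

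**Working it through.** **Step 1: item check.** The protocol states no sample size, event rate or effect size, so there is no figure of its own to reproduce. The check is of the variable list.

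| Needed for adjustment | Direct item | Partial proxy on the list |
|---|---|---|
| Comorbidity or operative risk | none | age; mRS at diagnosis |
| Disability before onset | none | mRS at diagnosis, which mixes prior and fistula-related disability |
| Reason for modality, or for no intervention | none | fistula level, feeder number and levels, Adamkiewicz involvement; centre; incidental presentation; free-text notes |

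**Step 2: possible bias from one unmeasured factor.** Let U be a binary poor-fitness indicator with prevalence p1 and p0 in the two groups and risk ratio R for a poor outcome. With no true treatment effect,

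apparent RR = [1 + p1(R − 1)] / [1 + p0(R − 1)].

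All inputs are assumptions; the protocol gives none.

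| p1 v p0 | R | Calculation | Apparent RR |
|---|---|---|---|
| 0.30 v 0.20 | 1.5 | 1.15 / 1.10 | 1.05 |
| 0.30 v 0.20 | 2.0 | 1.30 / 1.20 | 1.08 |
| 0.30 v 0.15 | 2.0 | 1.30 / 1.15 | 1.13 |
| 0.50 v 0.20 | 2.0 | 1.50 / 1.20 | 1.25 |
| 0.40 v 0.15 | 2.5 | 1.60 / 1.225 | 1.31 |
| 0.50 v 0.10 | 3.0 | 2.00 / 1.20 | 1.67 |

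For an adjusted analysis, p1 and p0 must be read as the prevalences that remain within levels of the adjusted covariates. The proxies act by narrowing that gap. At R = 2, shrinking it from 0.50 v 0.20 to 0.30 v 0.20 takes the spurious RR from 1.25 to 1.08.

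**Step 3: effect of sample size.** Assume a poor-outcome risk of 0.30 without U, U in 20% of one group and 30% to 50% of the other, R of 1.5 to 2.0, no true treatment effect, and a two-sided pooled two-proportion test at 0.05.

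| Patients per group | False-positive rate across the range |
|---|---|
| 100 | 5.6% to 25% |
| 250 | 6.5% to 54% |
| 500 | 7.9% to 83% |

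Worked example for the top of the range at 500 per group:

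- The risks are 0.30 × 1.5 = 0.45 and 0.30 × 1.2 = 0.36, a difference of 0.09.
- The pooled standard error is √(0.405 × 0.595 × 2/500) = 0.0310, so the critical difference is 1.96 × 0.0310 = 0.0609.
- The unpooled standard error is √[(0.45 × 0.55 + 0.36 × 0.64)/500] = 0.0309.
- Φ[(0.09 − 0.0609)/0.0309] ≈ 0.83.

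If U were recorded and correctly adjusted for, the RR would return to 1.00 and the rate to 5%.

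**The case against.** The strongest reply is that the list is less bare than the three absences suggest. The mRS at diagnosis already includes any pre-existing disability. The anatomical items bear on endovascular feasibility. Centre is recorded, and the Background section's only remark on why treatment varies points to differences across institutions. Incidental presentation may explain some conservative management. The premise that fitness and feasibility drive the choice is clinical judgement, not something the protocol states. Pre-onset mRS is hard to assign retrospectively in a disease of insidious onset, and some confounding by indication remains in any retrospective comparison.

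Most of this stands, and it limits the point. A reader might infer that adjusting for every listed item still leaves the main confounders out altogether. The list does not support that: they are partly measured. A reader might also infer that the gap cannot be repaired after the deadline. The protocol does not say so: the data come from existing records, centres keep their own data, and nothing rules out supplementary extraction. Nor is the whole of objective 2 equally affected, because no route from fitness to angiographic occlusion has been shown.

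The reply does not make the proxies sufficient. Age is a weak marker of fitness, mRS at diagnosis cannot separate prior from fistula-related disability, and an unstructured notes field is not a usable covariate. Some 'unknown' entries are better than having the item for no patient.

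**Conclusion.** The point holds as a limited one. None of the three items is on the list, and comparing modalities is a primary objective. Adjustment for what is collected can reduce confounding by indication but not remove it. The exposure is greatest for functional outcome, complications and contrasts with conservative management. The descriptive objectives are unaffected.

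The size of the bias cannot be derived from the document. The range of about 1.05 to 1.67 rests on assumed prevalences and risk ratios for a wholly unmeasured factor, with no true treatment effect. It should not be read as an estimate of the bias left after full adjustment, which falls to the extent that age, mRS at diagnosis, anatomy and centre capture the factor. The false-positive rates carry the same assumptions.

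**What to change.** Before data collection closes at the end of February 2026:

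1. Add structured columns, each with an 'unknown' option, for comorbidity or anaesthetic risk class and, where the chart states it, pre-onset mRS. Include both in the adjusted modality model with age, mRS at diagnosis, anatomy and centre.
2. Add a column for the main reason for the initial modality, including the reason for conservative management. Use it for description and a sensitivity analysis only. It should not define the main comparison set: it rests on retrospective judgement, and a set restricted to embolisation or surgery where both were feasible would leave patients with no stated reason, and those managed conservatively, without a place.
3. Describe the modality comparison as associational, and report a sensitivity analysis for unmeasured confounding, for example the Step 2 formula over a stated grid.

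If the columns cannot be added in time, item 3 still applies, with the residual confounding stated as a limitation.

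The cost is three columns from existing records, with no patient contact. Centres that have already started would have to go back to charts, some local approvals may need checking, and entries will be incomplete.

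### Initial treatment modality does not say whether combined treatment means planned or rescue; if rescues are coded as combined, single-modality results are flattered in primary objective 2

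*Protocol*

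**What the plan says.** Under Treatment Details (Data Collection and Variables), the protocol lists one field that assigns patients to treatment groups, headed "Initial treatment modality". Its options are "Endovascular embolization alone", "Open surgery alone", "Combined approaches" and conservative management. It gives no definition of alone or combined and no time window.

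These groups carry primary objective 2: "To compare treatment strategies (endovascular, surgical, combined, or conservative management) and their angiographic and clinical outcomes". The Statistical Analysis Plan section adds: "Comparative analyses will be performed to evaluate outcomes across treatment modalities using appropriate statistical tests". The primary outcomes are angiographic success and function at last follow-up (mRS and the Modified Aminoff–Logue scales).

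The same section of the protocol also lists:

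- number of embolisation attempts, with an angiographic outcome and complications for embolisation;
- a separate outcome and separate complications for surgery;
- a block on recurrence and re-treatment: occurrence, time, modality used for the recurrence, and angiographic outcome after re-treatment;
- one year of treatment and one time from diagnosis to first treatment.

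None of these fields records which modality came first, or whether a second was planned before the first was performed.

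**The concern.** The heading points to the first treatment. The word alone points to the whole course, because in its ordinary sense it is settled only when it is known that no other modality followed. A patient whose embolisation fails and who then has surgery can therefore be coded in two ways, and the protocol does not choose between them.

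Under the whole-course reading, that patient is combined. Membership of the embolisation-alone group then depends partly on whether embolisation worked, which is one of the outcomes being compared. The group keeps its successes and loses some of its failures, and the combined group becomes a mixture of planned staging and rescue. Surgery followed by embolisation is affected in the same way. Covariate adjustment does not repair groups formed on the outcome.

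The protocol relies on predefined options to keep sites consistent. For this field they leave room for sites to differ, so part of any difference between modalities could reflect local coding habit.

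**Working it through.** **No figure to reproduce.** The protocol states no closure rate, conversion rate, sample size, alpha or power. The check is a reading of the fields, followed by an illustration on assumed inputs.

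**Step 1. Where can a failed embolisation followed by surgery be entered?**

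- *Following the heading:* the patient stays under embolisation. The later surgery then has no clear place as re-treatment, because that block is framed around recurrence and a fistula that was never closed has not recurred.
- *Following the option wording:* the patient is not embolisation alone, and combined is the category that fits.

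Both entries are compatible with the text; the second sits more easily with the options offered.

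**Step 2. Can the other fields undo this?** In part. Embolisation closure and complications can be tabulated over everyone embolised, and surgical results over everyone operated on. But a patient coded combined, with partial occlusion after embolisation and successful surgical disconnection, could be a planned two-stage treatment or a rescue. Function is recorded once per patient at last follow-up, so separate procedure outcomes do not show which group that result belongs to.

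**Step 3. Illustration.** Let p be the true closure rate among patients who start with embolisation, and f the share of failures that go on to surgery and are also coded as combined. Both are assumptions. Then

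apparent closure in embolisation alone = p / (p + (1 − p)(1 − f)).

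With p = 0.70:

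- f = 0: 0.70 / 1.00 = 70%
- f = 0.5: 0.70 / (0.70 + 0.30 × 0.5) = 0.70 / 0.85 = 82.4%
- f = 0.8: 0.70 / (0.70 + 0.30 × 0.2) = 0.70 / 0.76 = 92.1%
- f = 1: 0.70 / 0.70 = 100%, as for any p

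Overstatement in percentage points for other inputs:

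| p | f = 0 | f = 0.25 | f = 0.5 | f = 0.75 |
|---|---|---|---|---|
| 0.5 | 0 | 7.1 | 16.7 | 30.0 |
| 0.7 | 0 | 5.7 | 12.4 | 20.3 |
| 0.9 | 0 | 2.3 | 4.7 | 7.3 |

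**Step 4. Effect on a comparison.** Assume 100 patients start with each modality, true closure is 70% in both, only embolisation failures are recoded, and the test is two-sided at 0.05. At f = 0.5 the comparison is 82.4% of 85 against 70% of 100. The chance of a significant difference is about 14% at f = 0.25, 50% at f = 0.5 and 93% at f = 0.75, although the modalities are equally effective.

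If surgical failures are recoded too, the bias is the difference between the two overstatements. Equal p and equal f cancel. With f = 0.5 in both, p = 0.70 for embolisation and 0.90 for surgery, the overstatements are 12.4 and 4.7 points. A true gap of 20 points then appears as 20 − (12.4 − 4.7) = 12.3 points. At equal f, over the p values in the table, the modality that fails more often gains more.

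**The case against.** The strongest reply is that no passage tells centres to code embolisation followed by surgery as combined. The heading says initial, and objective 2 speaks of strategies. On that reading alone and combined describe the plan at the outset, a failed embolisation stays where it started, and the bias is zero. This stands: a reader might infer that the groups are defined by later events and that embolisation success is therefore overstated, but the protocol establishes neither.

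A reader might also infer that complications of converted embolisations drop out of the embolisation rate. The documents do not support that. Complications are listed separately for each modality, and the secondary outcome is "Complication rates by treatment modality", so that rate can be computed over all embolised patients. Modality-specific closure can be recovered likewise.

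The re-treatment block could be used for rescue surgery, but its fields ask about recurrence and centres are not told to use it for a fistula that never closed. The extraction spreadsheet is not shown and may carry definitions. The grouping rule itself could be left to an analysis plan. Order and intent could not: if they are not collected, an analysis plan cannot fully restore them.

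Finally, both inputs to the illustration are assumed, and f requires both conversion and a particular coding choice. This stands too.

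**Conclusion.** The point holds as a conditional risk created by an undefined field. Under one permissible coding, failures leave the single-modality groups and the comparison by group in primary objective 2 is biased in their favour. Under the other the bias is zero, and mixed coding makes the groups inconsistent between sites.

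At an assumed 70% true closure, the overstatement for embolisation alone is 0 points with no recoding, about 12 with half of failures recoded and about 22 with 80% recoded (92.1 − 70). The documents allow no narrower statement, and these figures should not be read as an estimate of bias in this registry. The effect on mRS and Aminoff–Logue has the same direction if patients whose first procedure failed end with worse function than those closed at once; its size cannot be derived here.

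Modality-specific closure and complication rates over all treated patients are recoverable. Grouping by first procedure, and the functional comparison that depends on it, are not fully recoverable from the listed fields. Because this concerns a primary objective and becomes hard to repair after extraction, it should be settled before data collection closes.

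**What to change.** Replace the single field by three items:

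- (a) first procedure attempted: embolisation (including aborted attempts), surgery, or none;
- (b) second modality planned before the first procedure: yes, no or unknown;
- (c) any later procedure of the other modality, with the interval and the reason: planned stage, incomplete closure, or recurrence.

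Add to the analysis section that the primary comparison of modalities groups patients by first procedure, with planned combined treatment as its own group. A conversion stays in its first-procedure group and counts there as not closed by that modality. Where planning is unknown, analyse by first procedure.

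The cost is a few extra columns, drawn mainly from the procedural reports the protocol already names as sources. The protocol is dated 20 December 2025 and collection ends at the end of February 2026, so centres that have started will have some re-extraction, in an unfunded study. Intent will be missing from some older records. If failures are at present coded as combined, the closure figures for the single modalities will look less favourable than under the current list.
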